#### **4.3.2.3.3 Burst Treatment**

In the case of increased disease activity, the patient will have the opportunity to receive burst treatment, in addition to the study treatment, during the defined burst treatment window (see [Figure 1](#)). The patient should return to the clinic, either at a scheduled study visit or unscheduled flare visit, to be evaluated and to receive an increase or new dose of oral prednisone as follows:

- Burst Window 1 (Weeks 0 to 10): An increase or new dose of oral prednisone up to 40 mg/day (or equivalent; see [Appendix 18](#))
- Burst Window 2 (Weeks 24 to 34): An increase or new dose in oral prednisone up to 20 mg/day (or equivalent; see [Appendix 18](#))

When using corticosteroids as a burst treatment, the investigator will temporarily increase the dose of corticosteroids and then taper the patient back down to their previous corticosteroid dose *used prior to the initiation of the burst*, all over the course of 2 weeks. Patients will continue to receive their designated dose of study treatment (see Section [4.3.2](#)) during the burst treatment. The previous corticosteroid dose is defined as the dose of corticosteroids taken for the 2 weeks prior to the burst (if the dose changed during the 2 weeks, the investigator may choose which dose to use). If the patient was not previously on corticosteroids, the investigator will taper the patient back off corticosteroids completely. If the patient was on a corticosteroid-tapering schedule at the time of the burst treatment, the investigator will revise the tapering schedule as necessary to meet the target OCS dose ( $< 10$  mg/day and  $\leq$  Day 1 dose) by the end of the taper window, *if clinically appropriate*.

Patients may receive corticosteroids for emergent illness other than SLE (*e.g.*, trauma, asthma) or if clinically warranted to prevent adrenal crisis (*e.g.*, prior to surgery). If possible, treatment in these cases should last no more than 7 days.

Any dose of steroid higher than the maximum burst levels above, any failure to taper the burst down to the previous level over the course of 2 weeks, or any necessity for additional burst treatments for increased SLE-related activity (either a second treatment within the burst window or a burst treatment outside the burst window), as determined by the investigator, will be recorded in the Steroid and immunosuppressant eCRF.

Use of burst therapy to treat worsening of lupus will be captured on the Adverse Event eCRF (see Section [5.3.5.9](#)). If any patient needs additional corticosteroids for any reason *that falls outside the permitted OCS rules stated above* (Sections [4.3.2.3.2](#) and [4.3.2.3.3](#)), the Medical Monitor needs to be informed and the reason recorded on the Corticosteroid Medication eCRF.

#### **4.3.2.3.4 Escape Therapy**

If an increase in immunosuppressive therapy (referred to as “escape therapy”) is deemed medically necessary due to increased SLE disease activity, the patient will be given escape therapy, which will be recorded on the Steroid and Immunosuppressant eCRF. Patients receiving the following escape therapies *may* be allowed to remain on study drug *after discussion with the Medical Monitor* but will be considered a protocol-defined “non-responder” in the primary analysis:

- IV or IM steroids (*at doses greater than 40 mg prednisone PO or equivalent*)
- OCS doses exceeding the limits described elsewhere in the protocol (*e.g., prednisone (or equivalent) doses of > 40 mg/day during the first 24 weeks of the study, or > 20 mg/day between Weeks 24 and 48*)
- New or increased doses of an immunosuppressant *or anti-malarial* medication up to the maximum allowed in the study (see Section 4.3.2.3)

NOTE: Combinations of immunosuppressant medications that are not allowed in the inclusion and exclusion criteria (see Section 4.1) are prohibited during the study (see Section 4.6.2).

Whenever possible, a patient being evaluated for escape therapy will undergo assessment at either an unscheduled or flare visit prior to the increase in immunosuppression in order to quantify and record the increased disease activity, unless this occurs at a scheduled study visit (see Appendix 1).

If the patient requires any further treatment for SLE activity beyond the escape therapy described above (e.g., prohibited medications as defined in Section 4.4.2 or any accepted immunosuppressive that exceeds the maximum dose as defined by the protocol, or any increase in therapy not approved by the Medical Monitor), the patient should stay in the study but will be discontinued from study treatment (see Section 4.6.2).

Use of escape therapy to treat worsening of lupus will be captured on the Adverse Event eCRF (see Section 5.3.5.9). If any patient needs additional corticosteroids for *this* or any other reason, the Medical Monitor needs to be informed and the reason recorded on the Corticosteroid Medication eCRF.

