Background SOC therapy may consist of an OCS (which must be stable for 2 weeks prior to screening, dose not to exceed 40 mg/day of prednisone or equivalent) and/or certain oral immunosuppressive regimens (which must be stable for 2 months prior to screening). All immunosuppressive and anti-malarial medication will be kept stable throughout the trial unless dose reductions are necessary due to toxicity. All patients receiving immunosuppressive treatments are also encouraged to be on supportive therapy (e.g., folic acid, calcium, vitamin D). For patients who are on angiotensin converting enzyme (ACE) inhibitors or angiotensin receptor blockers (ARBs) at study entry, doses of ACE inhibitors or ARBs should be kept stable for at least 10 days prior to randomization and throughout the trial whenever possible. *It is strongly recommended that ACE inhibitors or ARBs not be initiated during the OCS stability windows.*

For patients on an OCS at baseline, there will be two, 12-week, OCS taper windows available to achieve the pre-specified OCS taper of < 10 mg/day prednisone or equivalent. The dose at the end of each OCS-stability window (i.e., the 12-week period immediately following the 12-week OCS taper window) will then be kept stable for an additional 12 weeks.

In the case of increased SLE disease activity, there can be two temporary increases in the corticosteroid dose, called “bursts,” that may be administered if needed. A burst may only be administered during a burst window (defined as the first 10 weeks of each OCS taper window)

and only once per window. A burst is defined as a temporary increase in corticosteroid dose (up to 40 mg/d prednisone or equivalent for Burst Window 1, and up to 20 mg/d prednisone or equivalent for Burst Window 2) with a taper back down to the dose immediately preceding the burst, all within a 2-week period.

If additional treatment is needed beyond the permitted burst therapy because of active SLE, as identified by the investigator, the patient may receive escape therapy; however, such patients will be considered trial-defined non-responders for the purposes of the primary analysis.

During taper, burst, and permitted escape therapies, patients will continue to receive their designated dose of study treatment.

Starting at the screening period, all patients must record their actual OCS use weekly, as instructed by study staff.

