### **Escape Therapy**

If an increase in immunosuppressive therapy (referred to as "escape therapy") is deemed medically necessary due to increased SLE disease activity, the patient will be given escape therapy, which will be recorded on the Steroid and Immunosuppressant eCRF. Patients receiving the following escape therapies, *may* be allowed to remain on study drug *after discussion with the Medical Monitor* but will be considered a protocol-defined "non-responder" in the primary analysis:

- IV or IM steroids (at doses greater than 40 mg prednisone PO or equivalent)

- OCS doses exceeding the limits described elsewhere in the protocol (*e.g.*, prednisone (or equivalent) doses of > 40 mg/day during the first 24 weeks of the study, or > 20 mg/day between Weeks 24 and 48)
- New or increased doses of an immunosuppressant or anti-malarial medication up to the maximum allowed in the study

NOTE: Combinations of immunosuppressant medications that are not allowed in the inclusion and exclusion criteria are prohibited during the study.

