Background SOC therapy may consist of an OCS (which must be stable for 2 weeks prior to screening, dose not to exceed 40 mg/day of prednisone or equivalent) and/or certain oral immunosuppression regimens (which must be stable for 2 months prior to screening; see Section [4.1.1](#)). All immunosuppressive and anti-malarial medication will be kept stable throughout the trial unless dose reductions are necessary due to toxicity. All patients receiving immunosuppressive treatments are also encouraged to be on supportive therapy (e.g., folic acid, calcium, vitamin D). For patients who are on angiotensin converting enzyme (ACE) inhibitors or angiotensin receptor blockers (ARBs) at study entry, doses of ACE inhibitors or ARBs should be kept stable for at least 10 days prior to randomization and throughout the trial whenever possible. *It is strongly recommended that ACE inhibitors or ARBs not be initiated during the OCS stability windows.*

For patients on an OCS at baseline, there will be two, 12-week, OCS taper windows available to achieve the pre-specified OCS taper of < 10 mg/day prednisone or equivalent (see [Appendix 4](#) and [Figure 1](#)). The dose at the end of each OCS-stability window (i.e., the 12-week period immediately following the 12-week OCS taper window) will then be kept stable for an additional 12 weeks. See Section [4.3.2.3](#) for more details.

In the case of increased SLE disease activity, there can be two temporary increases in the corticosteroid dose, called “bursts,” that may be administered if needed ([Figure 1](#)). A burst may only be administered during a burst window (defined as the first 10 weeks of each OCS taper window) and only once per window (see Section [4.3.2.3.3](#)). A burst is defined as a temporary increase in corticosteroid dose (up to 40 mg/d prednisone or equivalent for Burst Window 1, and up to 20 mg/d prednisone or equivalent for Burst Window 2) with a taper back down to the dose immediately preceding the burst, all within a 2-week period.

If additional treatment is needed beyond the permitted burst therapy because of active SLE, as identified by the investigator, the patient may receive escape therapy; however, such patients will be considered trial-defined non-responders for the purposes of the primary analysis (see Section 4.3.2.3.4).

[figure not shown]
During taper, burst, and permitted escape therapies, patients will continue to receive their designated dose of study treatment (see Section 4.3.2).

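### The escape-therapy list in Section 4.3.2.3.4 is narrower than the non-response rule in Section 3.1.1: low-dose IV/IM steroid is missed outright, and off-rule oral steroid within the dose caps is left unclear

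*Combined protocol and SAP*

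**What the plan says.** **The general rule.** Section 3.1.1 and the matching synopsis text start from need: "If additional treatment is needed beyond the permitted burst therapy because of active SLE", then "the patient may receive escape therapy; however, such patients will be considered trial-defined non-responders for the purposes of the primary analysis". No dose threshold is attached. A permitted burst is an oral increase given in a burst window, "defined as the first 10 weeks of each OCS taper window) and only once per window". That means Weeks 0 to 10 and Weeks 24 to 34. The dose is capped at 40 mg/day in the first window and 20 mg/day in the second, and must return to the pre-burst dose within 2 weeks.

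**The list.** Section 4.3.2.3.4 attaches primary non-response to named escape therapies:
- "IV or IM steroids (at doses greater than 40 mg prednisone PO or equivalent")
- "OCS doses exceeding the limits described elsewhere in the protocol", followed by "e.g., prednisone (or equivalent) doses of > 40 mg/day during the first 24 weeks of the study, or > 20 mg/day" for Weeks 24 to 48
- a new or increased immunosuppressant or anti-malarial.

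**Off-rule bursts.** Section 4.3.2.3.3 names a dose above the burst maximum, "any failure to taper the burst down to the previous level over the course of 2 weeks", a second burst in a window, and a burst outside a window. It requires them to be recorded and gives them no response status.

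**Related text.** Section 4.3.2.3.2 makes a breach of the oral corticosteroid (OCS) rules non-response for the endpoints that require the taper, and is silent on the primary. Section 4.4.2 prohibits IV/IM steroid only above 40 mg equivalent, except as escape. The SRI-4 definition in 4.5.8.9 and the primary analysis in 6.4.1 contain no treatment criterion. Section 6 leaves scoring detail to the DAP.

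**The concern.** The two sections draw the line on different grounds. Section 3.1.1 turns on whether the treatment was a permitted burst, which involves route, timing, number, duration and dose. The steroid items in 4.3.2.3.4 turn on dose. A programmer who derives responder status from the list could therefore score as responders some patients whom 3.1.1 calls non-responders.

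Such a patient must still meet the SLEDAI-2K, BILAG and PGA criteria at the visit, but added steroid makes that easier. The protocol itself says (3.3.6.2, 3.3.6.3) that corticosteroids can inflate comparator response and hide an efficacy signal. At stake are the Week 48 primary endpoint and the Week 24 SRI-4 response. The interim analysis is timed on the Week 24 evaluation, with futility criteria left to the DAP.

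**Working it through.** **1. The same cases under both sections**

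| Treatment given for SLE activity | Section 3.1.1 | Section 4.3.2.3.4 list |
|---|---|---|
| IV or IM steroid, 40 mg equivalent or less | Not an oral burst: non-response | Not listed, and not prohibited by 4.4.2 |
| Entry at 40 mg/day, tapered by Appendix 4 to below 10 mg/day by Weeks 11–12, raised to 40 mg/day at Week 14 | Outside any burst window: non-response | 40 is not above 40: missed if the caps are the limits |
| 20 mg/day started at Week 44 | Outside any burst window: non-response | 20 is not above 20: missed if the caps are the limits |
| Second burst in a window, or burst not tapered in 2 weeks, within the cap | Beyond the permitted burst: non-response | Missed if the caps are the limits |
| Oral dose above 40 mg/day before Week 24, or above 20 mg/day after | Beyond the permitted burst: non-response | Listed: non-response |

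The examples do not follow the windows. The 40 mg/day cap runs to Week 24, which is 24 − 10 = 14 weeks past Burst Window 1. The 20 mg/day cap runs to Week 48, which is 48 − 34 = 14 weeks past Burst Window 2. Calendar time outside burst windows is 48 − 20 = 28 of 48 weeks; this is not a share of patients.

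**2. Whether another section closes the gap**
- 4.4.1 makes new or increased immunosuppressants non-response, but 4.3.2.3.1 treats that class as excluding corticosteroids. Reading steroids into it would also fail permitted bursts.
- 4.6.2 stops study drug for new or increased SLE treatment that is not permitted and approved. It sets no responder status, and those patients continue scheduled visits, so they need not be missing.
- 6.1 treats patients without post-baseline response assessments as non-responders and says nothing on rescue.

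**3. Scale**

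Inputs from 6.1: 80 per arm, 50% against 75%, two-sided 0.05, stated power about 88%. An exact Fisher calculation gives 88.3% and a continuity-corrected normal approximation 88.2%, so the stated figure reproduces. The planned test is a stratified Cochran-Mantel-Haenszel (CMH); Fisher is used here for scale only.

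- One patient: 1/80 = 1.25 points. At the interim, with 50 to 80 per arm: 1/80 = 1.25 to 1/50 = 2.0 points.
- 95% CI half-width at the design rates: 1.96 × √(0.5 × 0.5/80 + 0.75 × 0.25/80) = 14.5 points.

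The documents give no rescue rates. Assume that 50% and 75% hold under the strict rule, and that scoring by the list adds 0 to 4 responders per 80:

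| Extra responders (placebo / active) | Rates | Difference (points) | Fisher power |
|---|---|---|---|
| 0 / 0 | 50% vs 75% | 25 | 88.3% |
| +1 / +1 | 51.25% vs 76.25% | 25 | 88.9% |
| +4 / +4 | 55% vs 80% | 25 | 90.6% |
| +1 / 0 | 51.25% vs 75% | 23.75 | 84.9% |
| +4 / 0 | 55% vs 75% | 20 | 71.2% |
| 0 / +1 | 50% vs 76.25% | 26.25 | 91.6% |
| 0 / +4 | 50% vs 80% | 30 | 97.5% |

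Equal reclassification leaves the difference unchanged. Only an imbalance between arms moves it, in either direction.

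**The case against.** The strongest reply is that the plan has one rule. Section 3.1.1 is express. Section 4.3.2.3.4 opens by defining escape therapy as an increase in immunosuppression needed for SLE activity, with no threshold. Its oral item refers to limits set elsewhere, which can include window, number and taper, and the caps are offered only as examples. Off-rule bursts also go on the same form as escape therapy: "the patient will be given escape therapy, which will be recorded on the Steroid and Immunosuppressant eCRF".

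For oral steroid this largely stands. A reader might infer that the protocol flatly contradicts itself on oral rescue, or that off-window rescue will be counted as response. The documents do not support that. The strict reading is the better one, and the other needs an illustration to be taken as exhaustive. The point is that nothing in 4.3.2.3.3, 4.3.2.3.4 or 6.4.1 rules the other out.

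For IV/IM steroid the reply fails. The threshold there is part of the item and is not an example.

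Three further replies carry weight. Section 4.6.2 may take such patients off study drug, which limits the scenario without deciding response. The DAP may already fix the rule. The trial is declared hypothesis-generating (6.4), and SRI-4 with a sustained low steroid dose is a secondary endpoint at both time points. That limits the damage but does not define the primary endpoint.

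**Conclusion.** The concern holds in a limited form. For IV/IM steroid of 40 mg or less, 3.1.1 and the list in 4.3.2.3.4 disagree directly. For off-window, repeat or un-tapered oral steroid within the caps, the text is ambiguous and favours non-response. In both cases a patient scored from the list could count as an SRI-4 responder at Week 48 and at Week 24.

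The size and direction of any effect are unknown. A reader might take the 71.2% power figure as an expected loss, or conclude that the result is biased for or against the drug. Neither follows: the counts are assumed, equal reclassification does no harm to power, and the documents give no rescue rates by arm.

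It should be fixed, because the primary endpoint needs one boundary set before unblinding. Confidence is medium, since the DAP has not been seen.

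**What to change.** In 4.3.2.3.4 and 6.4.1, and in the DAP, keep the existing dose caps and the immunosuppressant and anti-malarial item. Deleting the caps would loosen the rule, because the list now makes a dose above 20 mg/day after Week 24 primary non-response. Add that primary non-response also includes:
- (a) IV or IM steroid at any dose given for SLE activity
- (b) oral steroid started or raised for SLE activity outside a burst window, a second burst in a window, or a burst not returned to the prior dose within 2 weeks.

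Apply the same rule to Week 24 SRI-4 for treatment given before Week 24. Exempt steroid for non-SLE illness, adrenal prophylaxis, and slowing or pausing a taper without raising the dose, provided the dose stays within the existing caps. Report a sensitivity analysis under the dose-cap-only reading, with by-arm counts of patients whose status differs between the two.

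**Cost.** The change is to wording and derivation. Steroid use and the reason for off-rule steroid are already collected, and what patients may receive does not change. Observed response rates may be slightly lower. If 50% and 75% were in fact rates under the dose-cap reading, losing 4 responders in 80 from each arm would give 45% against 70% and Fisher power of 86.2%. Small off-window increases for SLE activity would count as non-response, as 3.1.1 already implies, even where 4.3.2.3.2 lets the investigator leave the held dose.

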#### **4.3.2.4 Background Standard of Care Therapy Compliance**

Starting at the screening period, all patients must keep a weekly diary of their actual OCS use as instructed by study staff. Patients will record their actual OCS dose on a weekly basis using a paper diary and as instructed by study staff. OCS usage will be recorded in the Corticosteroid Medication eCRF.

#### **4.3.3 Investigational Medicinal Product Accountability**

All IMPs required for completion of this study (GDC-0853 50-mg tablet and placebo tablet) will be provided by the Sponsor where required by local health authority

regulations. The study site will acknowledge receipt of IMPs using the IxRS to confirm the shipment condition and content. Any damaged shipments will be replaced.

IMPs either will be disposed of at the study site according to the study site's institutional standard operating procedure or will be returned to the Sponsor with the appropriate documentation. The site's method of IMP destruction must be agreed to by the Sponsor. The site must obtain written authorization from the Sponsor before any IMP is destroyed, and IMP destruction must be documented on the appropriate form.

Accurate records of all IMPs received at, dispensed from, returned to, and disposed of by the study site should be recorded on the Drug Inventory Log.

#### **4.3.4 Post-Trial Access to GDC-0853**

Patients may be screened for enrollment into an OLE study. *If they meet all OLE eligibility criteria, they may be enrolled if considered appropriate for participation,* according to the investigator.

Currently, the Sponsor (Genentech, a member of the Roche Group) does not have any plans to provide GDC-0853 or any other study treatments or interventions to patients who have completed the study and are not qualified or elect not to enter an OLE study, if available, in accordance with the Roche Global Policy on Continued Access to Investigational Medicinal Product, available at the following Web site:

[http://www.roche.com/policy\\_continued\\_access\\_to\\_investigational\\_medicines.pdf](http://www.roche.com/policy_continued_access_to_investigational_medicines.pdf)

#### **4.4 CONCOMITANT THERAPY, PROHIBITED FOOD, AND ADDITIONAL RESTRICTIONS**

Concomitant therapy includes any medication (e.g., prescription drugs, over-the-counter drugs, vaccines, herbal or homeopathic remedies, nutritional supplements) used by a patient from 7 days prior to initiation of study drug through 8 weeks after the last dose of study drug or entrance into an OLE, if initiated, whichever occurs first. All concomitant medication taken during the study must be documented on the eCRF along with indication, daily dose, and start and stop dates of administration. Adverse events related to the administration of a concomitant medication or the performance of a procedure must also be documented on the appropriate adverse event page of the eCRF.

It is recommended that patients avoid changing other *concomitant* prescription or non-prescription drugs, vitamins, and dietary supplements within 7 days or 5 half-lives, whichever is longer, prior to the first dose of study medication and throughout the study.

##### **4.4.1 Permitted Therapy**

Note for all concomitant immunosuppressive and anti-malarial medications: reductions to the concomitant immunosuppressive medication dose will not be allowed except in the case of intolerance or toxicity or for the safety of the patient, as determined by the investigator; any changes in the doses of concomitant immunosuppressive and anti-

malarial medications must be discussed in advance with the Medical Monitor unless medically emergent. Patients who require a new or increased dose of concomitant immunosuppressive medications will be considered protocol-defined non-responders (see Section [4.3.2.3](#)).

Addition, discontinuation, and dose adjustment of concomitant medications for conditions other than SLE are discouraged but permitted when required for the safe and effective treatment of patients.

Any case of medication intolerance or toxicity must be recorded as an adverse event and any dose modification recorded in the eCRF.

Certain combinations of the SLE therapies below are not permitted (see Section [4.1](#))

